## **8.2.2 Patient-reported Outcomes**

Not applicable.

## **8.3 Safety Assessments**

Details regarding specific safety procedures/assessments to be performed in this study are provided. The total amount of blood to be drawn over the course of the study (from prestudy to poststudy visits), including approximate blood volumes drawn by visit and by sample type per participant, can be found in the Procedures Manual.

Planned time points for all safety assessments are provided in the SoA.

### **8.3.1 Physical Examinations**

Investigators should pay special attention to clinical signs related to previous serious illnesses.

#### **8.3.1.1 Full Physical Examination**

The investigator or medically qualified designee (consistent with local requirements) will perform a complete physical examination per institutional standards during the Screening period. Height and weight will also be measured and recorded. Clinically significant abnormal findings should be recorded as medical history. The time points for full physical examinations are described in Section 1.3 (SoA). After the first dose of study intervention, new clinically significant abnormal findings should be recorded as AEs.

In pediatric participants, height and weight will be measured at every visit. In adult participants, height will be measured at Screening only and weight will be measured at every visit.

#### **8.3.1.2 Directed Physical Examination**

For cycles that do not required a full physical examination, as defined in Section 1.3 (SoA), the investigator or medically qualified designee (consistent with local requirements) will perform a directed physical examination per institutional standard prior to the administration of the study intervention, as clinically indicated. New clinically significant abnormal findings should be recorded as AEs.

### **8.3.2 Vital Signs**

Vital signs (body temperature [in centigrade], pulse rate [beats per minute], respiratory rate [per minute], and systolic and diastolic blood pressure [mmHg]) will be assessed by the investigator or medically qualified designee (consistent with local requirements) as specified

in Section 1.3 (SoA). Blood pressure and pulse rate will be measured after the participant has been resting for 5 minutes. All blood pressure measurements should be performed on the same arm, preferably by the same person. After the first dose of study intervention, new clinically significant abnormal findings should be recorded as AEs.

### **8.3.3 Electrocardiograms (ECG)**

A standard 12-lead ECG will be obtained and reviewed by an investigator or medically qualified designee (consistent with local requirements) at Screening. Participants must be in the recumbent position for a period of 5 minutes prior to the ECG. Clinically significant abnormal findings should be recorded as medical history. Assessments may be repeated during the study, as clinically indicated.

Note: A 6-lead ECG is allowed per institutional standard.

### **8.3.4 Clinical Safety Laboratory Assessments**

Refer to Appendix 2 for the list of clinical laboratory tests to be performed and to the SoA for the timing and frequency.

- The investigator or medically qualified designee (consistent with local requirements) must review the laboratory report, document this review, and record any clinically relevant changes occurring during the study in the AE section of the case report form (CRF). The laboratory reports must be filed with the source documents. Clinically significant abnormal laboratory findings are those which are not associated with the underlying disease, unless judged by the investigator to be more severe than expected for the participant's condition.
- All protocol-required laboratory assessments, as defined in Appendix 2, must be conducted in accordance with the Procedures Manual and the SoA.
- If laboratory values from nonprotocol specified laboratory assessments performed at the institution's local laboratory require a change in study participant management or are considered clinically significant by the investigator (eg, SAE or AE or dose modification), then the results must be recorded in the appropriate CRF (eg, SLAB).
- For any laboratory tests with values considered clinically significantly abnormal during participation in the study or within 30 days after the last dose of study intervention, every attempt should be made to perform repeat assessments until the values return to normal or baseline or if a new baseline is established as determined by the investigator.

Details regarding specific laboratory procedures/assessments to be performed in this study are provided below. The total amount of blood/tissue to be drawn/collected over the course of the study (from prestudy to poststudy visits), including approximate blood/tissue volumes drawn/collected by visit and by sample type per participant can be found in the Study Procedures Manual.

Refer to Section 1.3 (SoA) for the timing of laboratory assessments.

#### **8.3.4.1 Laboratory Safety Evaluations (Hematology, Chemistry and Urinalysis)**

Laboratory tests for hematology, chemistry, and urinalysis are specified in Appendix 2.

#### **8.3.4.2 Pregnancy Test**

All women who are being considered for participation in the study, and who are not surgically sterilized or postmenopausal, must be tested for pregnancy within 72 hours prior to C1D1. If a urine test is positive or not evaluable, a serum test will be required. Participants must be excluded/discontinued from the study in the event of a positive test result. Repeated pregnancy test should be conducted according to Section 1.3 (SoA) and as required by local guidelines. Refer to Appendix 5.

#### **8.3.5 Performance Assessments**

The performance scale to be used is dependent upon age: Lansky Play-Performance Scale (LPS) for participants up to and including 16 years of age; ECOG for participants >16 years of age. The performance scale used for a given participant at baseline will be the performance scale used throughout the study.

##### **8.3.5.1 Eastern Cooperative Oncology Group (ECOG) Performance Scale**

The investigator or medically qualified designee (consistent with local requirements) will assess ECOG status (refer to Appendix 9) at the time points specified in Section 1.3 (SoA). The ECOG status must be assessed within 3 days prior to C1D1.

##### **8.3.5.2 Lansky Play-Performance Scale (LPS)**

The LPS score is a standard way of measuring the functionality of pediatric participants up to and including the age of 16 years. The LPS is rated by parents based on their child's activity over the past week. Parents fill out the assessment based on the directions on the form, and the form is re-administered over time to assess for changes in performance status. A higher score means the child is functioning better. See Appendix 9 for a description of the full scale. The LPS will be assessed as specified in Section 1.3 (SoA).

#### **8.4 Adverse Events (AEs), Serious Adverse Events (SAEs), and Other Reportable Safety Events**

The definitions of an AE or SAE, as well as the method of recording, evaluating, and assessing causality of AE and SAE and the procedures for completing and transmitting AE, SAE, and other reportable safety event reports can be found in Appendix 3.

Progression of the cancer under study is not considered an AE as described in Section 8.4.6 and Appendix 3.

Adverse events, SAEs, and other reportable safety events will be reported by the participant (or, when appropriate, by a caregiver, surrogate, or the participant's legally authorized representative).

The investigator and any designees are responsible for detecting, documenting, and reporting events that meet the definition of an AE or SAE as well as other reportable safety events. Investigators remain responsible for following up AEs, SAEs, and other reportable safety events for outcome according to Section 8.4.3.

The investigator, who is a qualified physician, will assess events that meet the definition of an AE or SAE as well as other reportable safety events with respect to seriousness, intensity/toxicity and causality.

#### **8.4.1 Time Period and Frequency for Collecting AE, SAE, and Other Reportable Safety Event Information**

All AEs, SAEs, and other reportable safety events that occur after the participant provides documented informed consent form is signed but before intervention allocation, must be reported by the investigator if the participant is receiving placebo run-in or other run-in treatment, if the event cause the participant to be excluded from the study, or is the result of a protocol-specified intervention, including, but not limited to washout or discontinuation of usual therapy, diet, or a procedure.

- All AEs from the time of intervention allocation through 30 days after cessation of study intervention must be reported by the investigator.
- All AEs meeting serious criteria, from the time of intervention randomization through 90 days after cessation of study intervention or 30 days after cessation of study intervention if the participant initiates new anticancer therapy, whichever is earlier, must be reported by the investigator.
- All pregnancies and exposure during breastfeeding, from the time of intervention randomization through the time required to eliminate systemic exposure after cessation of study intervention as described in Sections 5.1, or 30 days after cessation of study intervention if the participant initiates new anticancer therapy must be reported by the investigator.
- Additionally, any SAE brought to the attention of an investigator at any time outside the time specified above must be reported immediately to the Sponsor if the event is considered related to study intervention.

Investigators are not obligated to actively seek AEs or SAEs or other reportable safety events in former study participants. However, if the investigator learns of any SAE, including a death, at any time after a participant has been discharged from the study, and he/she considers the event to be reasonably related to the study intervention or study participation, the investigator must promptly notify the Sponsor.

All initial and follow-up AEs, SAEs, and other reportable safety events will be recorded and reported to the Sponsor or designee within the time frames as indicated in [Table 7](#).

Table 7 Reporting Time Periods and Time Frames for Adverse Events and Other Reportable Safety Events

Type of Event	Reporting Time Period: Consent to Randomization/ Allocation	Reporting Time Period: Randomization/ Allocation through Protocol- specified Follow-up Period	Reporting Time Period: After the Protocol- specified Follow-up Period	Time Frame to Report Event and Follow-up Information to Sponsor:
Nonserious Adverse Event (NSAE)	Report if: - due to protocol-specified intervention - causes exclusion - participant is receiving placebo run-in or other run-in treatment	Report all	Not required	Per data entry guidelines
Serious Adverse Event (SAE) including Cancer and Overdose	Report if: - due to protocol-specified intervention - causes exclusion - participant is receiving placebo run-in or other run-in treatment	Report all	Report if: - drug/vaccine related. (Follow ongoing to outcome)	Within 24 hours of learning of event
Pregnancy/Lactation Exposure	Report if: - due to intervention - causes exclusion	Report all	Previously reported – Follow to completion/termination; report outcome	Within 24 hours of learning of event
Event of Clinical Interest (require regulatory reporting)	Report if: - due to intervention - causes exclusion	Report - potential drug-induced liver injury (DILI) - require regulatory reporting	Not required	Within 24 hours of learning of event
Event of Clinical Interest (do not require regulatory reporting)	Report if: - due to intervention - causes exclusion	Report - non-DILI ECIs and those not requiring regulatory reporting	Not required	Within 5 calendar days of learning of event

#### 8.4.2 Method of Detecting AEs, SAEs, and Other Reportable Safety Events

Care will be taken not to introduce bias when detecting AEs and/or SAEs and other reportable safety events. Open-ended and nonleading verbal questioning of the participant is the preferred method to inquire about AE occurrence.

#### **8.4.3 Follow-up of AE, SAE, and Other Reportable Safety Event Information**

After the initial AE/SAE report, the investigator is required to proactively follow each participant at subsequent visits/contacts. All AEs, SAEs, and other reportable safety events including pregnancy and exposure during breastfeeding, events of clinical interest (ECIs), cancer, and overdose will be followed until resolution, stabilization, until the event is otherwise explained, or the participant is lost to follow-up (as defined in Section 7.3). In addition, the investigator will make every attempt to follow all nonserious AEs that occur in randomized participants for outcome. Further information on follow-up procedures is given in Appendix 3.

#### **8.4.4 Regulatory Reporting Requirements for SAE**

Prompt notification (within 24 hours) by the investigator to the Sponsor of SAE is essential so that legal obligations and ethical responsibilities towards the safety of participants and the safety of a study intervention under clinical investigation are met.

The Sponsor has a legal responsibility to notify both the local regulatory authority and other regulatory agencies about the safety of a study intervention under clinical investigation. The Sponsor will comply with country-specific regulatory requirements and global laws and regulations relating to safety reporting to regulatory authorities, IRB/IECs, and investigators.

Investigator safety reports must be prepared for suspected unexpected serious adverse reactions (SUSARs) according to local regulatory requirements and Sponsor policy and forwarded to investigators as necessary.

An investigator who receives an investigator safety report describing an SAE or other specific safety information (eg, summary or listing of SAE) from the Sponsor will file it along with the IB and will notify the IRB/IEC, if appropriate according to local requirements.

#### **8.4.5 Pregnancy and Exposure During Breastfeeding**

Although pregnancy and infant exposure during breastfeeding are not considered AEs, any pregnancy or infant exposure during breastfeeding in a participant (spontaneously reported to the investigator or their designee) that occurs during the study are reportable to the Sponsor.

All reported pregnancies must be followed to the completion/termination of the pregnancy.

Any pregnancy complication will be reported as an AE or SAE.

The medical reason (example: maternal health or fetal disease) for an elective termination of a pregnancy will be reported as an AE or SAE. Prenatal testing showing fetus will be born with severe abnormalities/congenital anomalies that leads to an elective termination of a pregnancy will be reported as an SAE for the fetus.

Pregnancy outcomes of ectopic pregnancy, spontaneous abortion, missed abortion, benign hydatidiform mole, blighted ovum, fetal death, intrauterine death, miscarriage, and stillbirth

must be reported as serious events (Important Medical Events). If the pregnancy continues to term, the outcome (health of infant) must also be reported.

#### **8.4.6 Disease-related Events and/or Disease-related Outcomes Not Qualifying as AEs or SAEs**

Efficacy endpoints as outlined in this section will not be reported to the Sponsor as described in Section 8.4.1.

Specifically, the suspected/actual events covered in this exception include any event that is disease progression of the cancer under study.

The Sponsor will monitor unblinded aggregated efficacy endpoint events and safety data to ensure the safety of the participants in the study. Any suspected endpoint that upon review is not progression of the cancer under study will be forwarded to Global Pharmacovigilance as an SAE within 24 hours of determination that the event is not progression of the cancer under study.

#### **8.4.7 Events of Clinical Interest (ECIs)**

Selected nonserious and SAEs are also known as ECIs and must be reported to the Sponsor.

Events of clinical interest for this study include:

1. An overdose of Sponsor's product, as defined in Section 8.5, that is not associated with clinical symptoms or abnormal laboratory results.
2. An elevated AST or ALT lab value that is greater than or equal to 3X the upper limit of normal and an elevated total bilirubin lab value that is greater than or equal to 2X the upper limit of normal and, at the same time, an alkaline phosphatase lab value that is less than 2X the upper limit of normal, as determined by way of protocol-specified laboratory testing or unscheduled laboratory testing.\*

\*Note: These criteria are based upon available regulatory guidance documents. The purpose of the criteria is to specify a threshold of abnormal hepatic tests that may require an additional evaluation for an underlying etiology. The study site guidance for assessment and follow up of these criteria can be found in the Investigator Study File Binder (or equivalent).

### **8.5 Treatment of Overdose**

For this study, an overdose of pembrolizumab will be defined as any dose of 1000 mg or greater ( $\geq 5$  times the indicated dose).

No specific information is available on the treatment of overdose of pembrolizumab. In the event of overdose, the participant should be observed closely for signs of toxicity. Appropriate supportive treatment should be provided if clinically indicated.

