#### 4.3.1 Maximum Dose/Exposure for This Study

The maximum dose/exposure of pembrolizumab allowed in this study is 200 mg Q3W in adult participants (or 2 mg/kg [up to 200 mg] Q3W in pediatric participants) for 35 administrations (approximately 2 years).

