## Demographics

5. Be male or female and at least 12 years of age, at the time of signing the informed consent/assent.

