## 6.1 Study Intervention(s) Administered

The study intervention to be used in this study is outlined in [Table 3](#).

Table 3 Study Interventions

Arm Name	Arm Type	Intervention Name	Type	Dose Formulation	Unit Dose Strength	Dosage Level(s)	Route of Administration	Regimen	Use	IMP/NIMP	Sourcing
Pembrolizumab	Experimental	Pembrolizumab (MK-3475)	Biological/Vaccine	Solution for Infusion	25 mg/mL vial	200 mg (adult participants) or 2 mg/kg (up to 200 mg - pediatric participants) on Day 1 of each cycle	IV Infusion	Q3W for up to 35 administrations (approximately 2 years)	Experimental	IMP	Provided centrally by the Sponsor
IMP=investigational medicinal product; IV=intravenous; NIMP=noninvestigational medicinal product; Q3W=every 3 weeks Definition Investigational Medicinal Product (IMP) and Non-Investigational Medicinal Product (NIMP) is based on guidance issued by the European Commission. Regional and/or Country differences of the definition of IMP/NIMP may exist. In these circumstances, local legislation is followed.											

All study interventions will be administered on an outpatient basis.

All products indicated in [Table 3](#) will be provided centrally by the Sponsor or locally by the study site, subsidiary or designee, depending on local country operational or regulatory requirements .

For any commercially available product that is provided by the study site, subsidiary, or designee, every attempt will be made to source these supplies from a single lot/batch number. The study site is responsible for recording the lot number, manufacturer, and expiry date for any locally purchased product as per local guidelines unless otherwise instructed by the Sponsor.

Refer to Section 8.1.8 for details regarding administration of the study intervention.

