### 9.11 Compliance (Medication Adherence)

Drug accountability data for study treatment will be collected during the study. Any deviation from protocol-directed administration will be reported.

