##### **Events meeting the AE definition**

- Any abnormal laboratory test results (hematology, clinical chemistry, or urinalysis) or other safety assessments (eg, ECG, radiological scans, vital signs measurements), including those that worsen from baseline, considered clinically significant in the medical and scientific judgment of the investigator.
- Exacerbation of a chronic or intermittent pre-existing condition including either an increase in frequency and/or intensity of the condition.
- New conditions detected or diagnosed after study intervention administration even though it may have been present before the start of the study.
- Signs, symptoms, or the clinical sequelae of a suspected drug-drug interaction.
- Signs, symptoms, or the clinical sequelae of a suspected overdose of either study intervention or a concomitant medication.
- For all reports of overdose (whether accidental or intentional) with an associated AE, the AE term should reflect the clinical symptoms or abnormal test result. An overdose without any associated clinical symptoms or abnormal laboratory results is reported using the terminology "accidental or intentional overdose without adverse effect."
- Any new cancer (that is not a condition of the study). Progression of the cancer under study is not a reportable event. Refer to Section 8.4.6 for additional details.

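### The study-wide 1000 mg overdose threshold equals five times plan only at a 200 mg dose, so an asymptomatic pediatric overdose below 1000 mg can miss event-of-clinical-interest status

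*Combined protocol and SAP*

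**What the plan says.** Section 8.5 states that for this study "an overdose of pembrolizumab will be defined as any dose of 1000 mg or greater", and adds in parentheses that this is at least 5 times the indicated dose. The same section asks for close observation after an overdose.

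The planned dose differs by age group. Adults receive 200 mg every three weeks. Section 4.3.1 sets the other maximum at "2 mg/kg [up to 200 mg] Q3W in pediatric participants", and Table 3 in Section 6.1 gives the same dose: "2 mg/kg (up to 200 mg - pediatric participants) on Day 1 of each cycle". These participants can enter the study, because the age criterion in Section 5.1 is "Be male or female and at least 12 years of age".

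Section 8.4.7 lists as its first event of clinical interest (ECI) an overdose of the Sponsor's product "as defined in Section 8.5, that is not associated with clinical symptoms or abnormal laboratory results". It is the only rule that cites Section 8.5. Appendix 3 (Sections 10.3.1 and 10.3.3) and Table 7 also use the word overdose but attach no amount to it. The country-specific requirements in Appendix 7 add nothing on this point.

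**The concern.** The threshold is written in milligrams and explained as a multiple. The two agree only when the planned dose is 200 mg. For a participant on a lower weight-based dose, 1000 mg is always at least five times plan, so nothing is over-classified. The reverse does not hold: a dose can be five or more times plan and still be under 1000 mg.

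The first ECI exists to catch overdoses that produce no symptoms and no laboratory change, and those are the events the milligram figure can miss. What could be lost is the ECI label, its reporting time frame in Table 7 (24 hours or 5 calendar days, depending on the row) and the Section 8.5 prompt to observe the participant closely. The event would not vanish from the record, since other reporting routes remain.

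**Working it through.** **Inputs**

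- Overdose threshold: 1000 mg, equated with at least 5 times the indicated dose (Section 8.5).
- Adult dose: 200 mg (Section 4.3.1).
- Pediatric dose: 2 mg/kg, capped at 200 mg (Sections 4.3, 4.3.1 and 6.1).
- Pediatric body weight: not given in the documents. The weights below are assumptions, shown as a range.

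**The plan's own figure.** For an adult, 5 × 200 mg = 1000 mg. The stated equivalence reproduces exactly.

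**Pediatric participants.** For weight W in kg, the planned dose is d = min(2W, 200) mg. Five times plan is 5d = min(10W, 1000) mg. Hence 5d is below 1000 mg if and only if W is below 100 kg, whereas 1000/d is at least 5 at every weight. The uncovered doses run from 5d to just under 1000 mg.

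| Assumed weight (kg) | Planned dose (mg) | Five times plan (mg) | 1000 mg as a multiple of plan | Uncovered range (mg) |
|---|---|---|---|---|
| 40 | 80 | 400 | 12.5 | 400 to <1000 |
| 45 | 90 | 450 | 11.1 | 450 to <1000 |
| 50 | 100 | 500 | 10.0 | 500 to <1000 |
| 60 | 120 | 600 | 8.3 | 600 to <1000 |
| 70 | 140 | 700 | 7.1 | 700 to <1000 |
| 80 | 160 | 800 | 6.25 | 800 to <1000 |
| 100 or more | 200 | 1000 | 5.0 | none |

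**A ten-fold dosing error.** In an adult this is 10 × 200 = 2000 mg, well above the threshold. In a pediatric participant under 100 kg it is 10d = 20W mg, which stays below 1000 mg whenever W is under 50 kg. At 45 kg it is 900 mg, at 49 kg 980 mg, and at 50 kg exactly 1000 mg.

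**What still captures such an event.** Section 10.3.1 counts as adverse events any signs, symptoms or "the clinical sequelae of a suspected overdose of either study intervention or a concomitant medication". That does not help when there are none. The same section says "An overdose without any associated clinical symptoms or abnormal laboratory results is reported using the terminology" it then supplies, but it gives no amount that makes a dose an overdose, so a site is left with the figure in Section 8.5. Section 9.11 says "Any deviation from protocol-directed administration will be reported", but it sets no time frame and confers no ECI status.

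**The case against.** The strongest reply is that the parenthesis already covers the case. If the indicated dose is read as each participant's own dose, five times 2 mg/kg is the pediatric threshold and the gap closes. That reading is possible, but the text does not state it. The operative definition is the milligram figure, and the indicated dose is not tied to an age group. Two sites could classify the same event differently.

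A second reply is that a fixed amount is defensible in itself, because it treats people of equal weight alike. At 60 kg, 1000 mg is 1000/60 = 16.7 mg/kg for an adolescent or an adult. A five-fold pediatric rule would call 600 mg an overdose in a 60 kg adolescent but not in a 60 kg adult. Section 4.3 also mentions adult trial regimens up to 10 mg/kg every two weeks. This would justify a purely absolute rule. It does not rescue a rule that presents its amount as a five-fold multiple, and the cited data concern dose and efficacy in melanoma and lung cancer trials, not adolescent safety.

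A third reply is that splitting the threshold into adult and pediatric parts needs an age boundary, which the dosing text does not give. That is true of the dosing rule already. Whichever planned dose a participant is assigned decides which threshold applies, so the split adds no new ambiguity.

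The point about reach stands in full. Section 2.2.1.2 describes the disease as exceptionally uncommon in children, and about 50 participants are planned in all. A missed event needs a pediatric participant under 100 kg, an error of at least five-fold that stays below 1000 mg, no symptoms or laboratory change, and a site applying only the milligram figure.

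**Conclusion.** The concern holds. Section 8.5 is wrong as written for pediatric participants under 100 kg: its amount and its stated multiple disagree, and the Section 8.4.7 rule for asymptomatic overdose inherits the disagreement. The inconsistency follows from the dosing rule alone. Only the illustrated ranges rest on assumed weights, and the reporting gap rests on the literal reading of the milligram figure. Severity is minor. The expected number of affected events is very low, the loss is one of classification, timeliness and the observation prompt, and no efficacy endpoint, estimate or analysis changes.

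**What to change.** Reword the definition in Section 8.5 along these lines: *an overdose is a dose of ≥1000 mg in adult participants, or ≥5 times the planned dose (≥10 mg/kg, maximum 1000 mg) in pediatric participants.* This keeps the sponsor's own five-fold multiple and leaves the adult rule unchanged. It moves the pediatric threshold to, for example, 400 mg at 40 kg, 600 mg at 60 kg and 1000 mg at 100 kg or more. Section 8.4.7 picks up the change through its cross-reference and needs no edit. The cost is one sentence, with no change to dosing, endpoints or analyses.
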